5.4.2 Additional Secondary Efficacy Endpoints

5.4.2.1 Proportion of Patients with A ≥ 2-step Improvement from Baseline on the ETDRS-DRSS over Time

The proportion of patients with \geq 2-step improvement from baseline on the ETDRS-DRSS over time will be analyzed using the analysis method, estimand and data handling rules following those for the main analysis for the primary endpoint (see Section 5.3) comparatively through Week 52 and with adjusted proportions descriptively through end of study.

5.4.2.2 Proportion of Patients with a ≥ 3-step Improvement from Baseline on the ETDRS-DRSS over Time

The proportion of patients with \geq 3-step improvement from baseline on the ETDRS-DRSS over time will be analyzed using analysis method, estimand and data handling rules as Section 5.4.1.5 comparatively through Week 52, and descriptively through end of study.

5.4.2.3 Time to First Development of Either PDR, ASNV, or CI-DME

The time to first development of either PDR, ASNV, or CI-DME will be analyzed using the same analysis method, estimand and data handling rules as Section 5.4.1.1 comparatively through Week 60, and will be estimated using the Kaplan-Meier approach through end of study.

5.4.2.4 Time to First Development of PDR or ASNV

The time to first development of PDR or ASNV will be analyzed using the same analysis method, estimand and data handling rules as Section 5.4.1.1 comparatively through Week 60, and will be estimated using the Kaplan-Meier approach through end of study.

5.4.2.5 Time to First Development of CI-DME

The time to first development of CI-DME will be analyzed using the same analysis method, estimand and data handling rules as Section 5.4.1.1 comparatively through Week 60, and will be estimated using the Kaplan-Meier approach through end of study.

5.4.2.6 Time to First Development of a ≥ 2-step Worsening from Baseline on the ETDRS-DRSS

The time to first development of a \geq 2-step worsening from baseline on the ETDRS DRSS will be analyzed using the same analysis method, estimand and data handling rules as Section 5.4.1.1 comparatively through Week 52, and will be estimated using the Kaplan-Meier approach through end of study.

5.4.2.7 Time to First Development of a ≥ 3-step Worsening from Baseline on the ETDRS-DRSS

The time to first development of a \geq 3-step worsening from baseline on the ETDRS DRSS will be analyzed using the same analysis method, estimand and data handling rules as Section 5.4.1.1 comparatively through Week 52, and will be estimated using the Kaplan-Meier approach through end of study.

5.4.2.8 Change from Baseline in BCVA As Measured on the ETDRS Chart over Time

This endpoint will be summarized using descriptive statistics for each study visit based on all observed data through the end of the study. This endpoint will also be analyzed using the mixed-effect model for repeated measures (MMRM) comparatively through Week 52 and through Week 60, and will be summarized using adjusted mean changes from the MMRM model through the end of the study.

The estimand for the endpoint will be as follows:

- Population: Adult patients with moderately severe or severe NPDR (ETDRS-DRSS level 47 or 53) and no presence of CI-DME who are naive to any treatment for DR in the study eye
- Variable: change from baseline in BCVA score over time
- Intercurrent events:
 - Receiving any supplemental treatment: A treatment policy strategy will be applied where all observed values will be used regardless of the occurrence of the intercurrent event.
 - Receiving any prohibited therapy or PRP regardless of study drug discontinuation status: A treatment policy strategy will be applied where all observed values will be used regardless of the occurrence of the intercurrent event.
 - Discontinuing study treatment (PDS arm) or discontinuing study (comparator arm) due to an AE: A treatment policy strategy will be

- applied where all observed values will be used regardless of the occurrence of the intercurrent event.
- Discontinuing study treatment (PDS arm) or discontinuing study (comparator arm) due to lack of efficacy per Investigator's judgment: A treatment policy strategy will be applied where all observed values will be used regardless of the occurrence of the intercurrent event.
- Population-level summary: Difference in adjusted mean between PDS and comparator arms grouped as assigned at randomization

All observed data will be included in the analysis regardless of whether or not a patient has experienced an intercurrent event. Missing data will be implicitly imputed by the MMRM model, assuming a missing-at-random (MAR) mechanism. The dependent variable in the MMRM model is the change from baseline in BCVA at post-baseline visits and the independent variables are the treatment group, time, treatment-by-time interaction, baseline BCVA letter score (continuous), and the randomization stratification factors of baseline ETDRS-DRSS level (47 vs. 53) and baseline intraretinal or subretinal fluid status (present vs. absent) as fixed effects. The MMRM model will assume an unstructured covariance structure. If there are convergence problems with the model, the following covariance structures will be implemented in order until convergence is achieved: first order antedependence, heterogeneous Toeplitz and first order autoregressive.

5.4.2.9 Proportion of Patients Who Lose < 15, < 10 and < 5 Letters in BCVA from Baseline over Time

The proportion of patients who lose < 15, < 10 and < 5 letters (defined as change from baseline > -15, > -10, > -5 letters respectively) in BCVA from baseline over time will be summarized comparatively through Week 52, and through Week 60, and descriptively through end of study. The analysis will use an unadjusted normal approximation for binomial proportions.

5.4.2.10 Proportion of Patients with a BCVA Score of 69 Letters (20/40 Approximate Snellen Equivalent) or Better over Time

The proportion of patients with a BCVA score of 69 letters (20/40 approximate Snellen equivalent) or better over time will be summarized comparatively through Week 52, and through Week 60, and descriptively through end of study. The analysis will use an unadjusted normal approximation for binomial proportions.

5.4.2.11 Change from Baseline in CST As Measured on SD-OCT over Time

The change from baseline in CST as measured on SD-OCT over time will be analyzed using the same methods described in Section 5.4.2.8, comparatively through Week 52, and through Week 60, and will be summarized using adjusted mean changes through end of study.

5.4.2.12 Change from Baseline in Total Macular Volume As Measured on SD-OCT over Time

The change from baseline in total macular volume as measured on SD-OCT over time is a continuous endpoint and will analyzed using the same methods described in Section 5.4.2.8, comparatively through Week 52, and through Week 60, and will be summarized using adjusted mean changes through end of study.

5.4.2.13 Proportion of Patients with Absence of Intraretinal Fluid, Subretinal Fluid or Both over Time

The proportion of patients with absence of intraretinal fluid, subretinal fluid and both intraretinal and subretinal fluid as assessed by SD-OCT (as measured in the central 1mm subfield) over time will be summarized comparatively through Week 52, and through Week 60, and descriptively through end of study. The analysis will use an unadjusted normal approximation for binomial proportions.

5.4.2.14 Proportion of Patients Who Do not Undergo Supplemental Treatment with Intravitreal Ranibizumab within Each Refillexchange Interval

This endpoint will be summarized descriptively during the entire study period and between each refill-exchange period for patients in the Safety-Evaluable Population. In order to avoid bias, the proportion of patients who do not undergo supplemental treatment will be evaluated using only the patients who were able to be assessed for the need for supplemental treatment, that is, patients who have the implant insertion with at least one visit in between implant insertion and first refill-exchange (or target day of first refill-exchange); or between two planned refill-exchanges in patients who had a refill-exchange at the start of the interval. This is the subset of patients who are assessed for the need of supplemental treatment at least once within a given refill-exchange interval.

At the final analysis additional summaries will be provided in the PDS Safety Population.

5.4.2.15 Proportion of Patients Who Report Preferring PDS Treatment to Intravitreal Ranibizumab Treatment, As Measured by the PPPQ at Week 52

The analysis of this endpoint is described in Section 5.7.6.1.

5.5 EXPLORATORY EFFICACY ENDPOINTS ANALYSIS

5.5.1 Change from Baseline in Total Area of Ischemic Non Perfusion within the Macula and Ischemic Non Perfusion within the Total Retinal Area over Time

The change from baseline in total area of ischemic non perfusion within the macula and ischemic non perfusion within the total retinal area over time will be analyzed using the same methods described in Section 5.4.2.8, comparatively through Week 52, and through Week 60, and will be summarized using adjusted mean changes through end of study.

Descriptive summaries will also present mean changes in the fellow eye, as well as the subgroup of patients never having received treatment in the fellow eye. Summaries will be presented comparatively through Week 52 and through Week 60, and overall through end of study, conditional on the availability of data at the time of reporting.

5.5.2 Time to First Vitrectomy for Complications of PDR

The time to first vitrectomy for complications of PDR will be analyzed using the same methods as Section 5.4.1.1 comparatively through Week 52, comparatively through Week 60, and using the Kaplan-Meier approach through end of study.

5.5.3 Time to First PRP

The time to first PRP will be analyzed using the same methods as Section 5.4.1.1 comparatively through Week 52, comparatively through Week 60, and using the Kaplan-Meier approach through end of study.

5.5.4 Proportion of Patients That Receive Supplemental Intravitreal Ranibizumab 0.5 Mg Injection after PDS Implant Insertion and Number of Supplemental Treatments Patients Receive

The proportion of patients that receive supplemental intravitreal ranibizumab 0.5 mg injection after the PDS implant insertion in the PDS Safety Population and number of supplemental treatments patients receive will be summarized descriptively through Week 52 (at primary analysis) and through the end of study (at final analysis) and between each refill-exchange. This endpoint is the complement of the secondary endpoint in Section 5.4.2.14.

5.5.5 Proportion of Patients in the Comparator Arm That Receive a Supplemental Intravitreal Ranibizumab 0.5 Mg Injection and the Number of Supplemental Treatments Patients Receive Prior to Week 52

The proportion of patients in the comparator arm Safety-Evaluable Population that receive a supplemental intravitreal ranibizumab 0.5 mg injection and the number of intravitreal treatments patients receive will be summarized descriptively through Week 52 (at primary analysis). The proportion of patients that receive an intravitreal ranibizumab 0.5 mg injection will be evaluated using only the patients who were able to be assessed for the need for supplemental treatment (those who are followed up to at least Week 4).

5.5.6 Evaluate Advanced Analytics Tools for the Assessment of Clinically Relevant Features

This analysis is planned in an exploratory fashion as the technology is in the early stages of development. Standard imaging analysis routinely performed by central reading center expert graders will continue to support the secondary objectives and endpoints outlined in Section 5.4. The evaluation of OCT and CFP with advanced analytics tools, such as machine learning and deep learning methods, are ongoing and

may help establish potential clinical use of this technology in the optimization of disease screening and early diagnosis, as well as prediction and monitoring of disease progression and treatment response. The analysis plan and analysis results for the advanced analytics will not be included in this SAP or the clinical study report (CSR), but will be provided separately.

5.6 SAFETY ANALYSES

Safety will be assessed through descriptive summaries of AEs, ADEs, ocular assessments, and ADAs to ranibizumab. Clinically significant laboratory abnormalities and clinically significant vital sign abnormalities will be reported as AEs and evaluated as part of the AE assessments.

Safety data will be summarized for the Safety-Evaluable Population at the time of the primary analysis through Week 52 and for the PDS Safety Population through the end of the study at the time of the final analysis (see Section 4) unless otherwise specified.

Safety summaries and listings in the Safety-Evaluable Population and in the PDS Safety Population will include data collected on or after Study Day 1 and PDS Day 1 respectively, which are defined as follows:

Table 2 Planned Safety Analyses

Population	Group	Data to be included in the analysis
Safety-Evaluable Population	PDS arm	Day of 1 st loading dose injection (Study Day 1) to Week 52 at the primary analysis
Safety-Evaluable Population	Comparator arm	Day of randomization (Study Day 1) to Week 52 at the primary analysis
PDS Safety Population	PDS arm	Day of 1st loading dose injection (PDS Day 1) through EOS at the final analysis
PDS Safety Population	Comparator arm	Day of 1st loading dose injection (PDS Day 1) (expected at the Week 60 visit) through EOS at the final analysis

CCOD = Clinical Cut-off date; EOS = End of Study; PDS =Port Delivery System with ranibizumab

For patients randomized to the comparator arm, only key safety events (SAEs from Protocol mandated interventions, SARS-CoV-2 related AEs, and AEs leading to study discontinuation, see Section 5.3.1 of the Protocol) will be collected until study treatment (first administration of intravitreal ranibizumab 0.5 mg either as a supplemental treatment or a loading dose) is initiated. Upon initiation of study treatment, all AEs will be reported until the patient's final study visit.

5.6.1 Extent of Exposure

Exposure to study treatment (number of study treatments [PDS refill-exchanges, intravitreal ranibizumab loading doses, supplemental intravitreal ranibizumab injections], duration of treatment) will be summarized by treatment group for the study eye in the Safety-Evaluable Population and in the PDS Safety Population according to the

schedule set in Table 2. Summaries will include the number of intravitreal injections prior to implant, and time to implant post randomization.

For the Safety-Evaluable Population PDS arm duration of treatment is the time from first study treatment (intravitreal ranibizumab injection as loading) to the earlier of:

- The date of treatment discontinuation or date of study termination
- The date of Week 52 visit.

For the PDS Safety Population, duration of treatment is the time from 1st loading dose injection to the earlier of:

- The date of treatment discontinuation or date of study termination
- The final study visit at final analysis.

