Patients randomized to the PDS arm will receive at least two loading doses with intravitreal ranibizumab 0.5 mg injections, administered at Day 1 and Week 4 visits. The first loading dose must be administered after the conclusion of the randomization visit assessments. At Week 4, patients must complete a pre-implant visit prior to the implant insertion surgery. Both visits must be completed within the Week 4 window and the PDS implant (pre-filled with ranibizumab 100 mg/mL) will be surgically inserted 1-14 days after the second loading dose (e.g., if the patient receives the second loading dose at Day 28 (Week 4), implant insertion surgery must occur no earlier than Day 29 and no later than Day 35). Patients will receive PDS implant refill-exchange procedures (ranibizumab 100 mg/mL) at Weeks 40, 76, 112, and Q36W thereafter (Visit Z refill-exchange visit) until the end of the study.

Patients in the PDS arm who meet specific clinical criteria (development of CI-DME or PDR/ASNV) per Investigator assessment can receive supplemental treatment with intravitreal ranibizumab 0.5 mg injections per Investigator's clinical judgment at any non–refill-exchange study visit during the study post implant (see Section 4.3.2.3 of the Protocol).

Patients randomized to the comparator arm will undergo study visits every 4 weeks (Q4W) for observation and comprehensive clinical monitoring. Beginning at Week 60, patients will receive two loading doses with intravitreal ranibizumab 0.5 mg injections, administered at the Week 60 and Week 64 visits. At Week 64, patients must complete a pre-implant visit prior to the implant insertion surgery. Both visits must be completed within the Week 64 window and the PDS implant (pre-filled with ranibizumab 100 mg/mL) surgically inserted 1-14 days after the Week 64 intravitreal injection. Patients will undergo a refill-exchange procedure with ranibizumab 100 mg/mL at Week 100 and Q36W thereafter (Visit Z refill-exchange visit) until the end of the study.

If PDS implant insertion surgery cannot be completed within the required timeframe (1-14 days after intravitreal ranibizumab 0.5 mg injection and within the study visit

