window) because of an extenuating circumstance, the PDS implant insertion may be postponed once for approximately 4 weeks following consultation with the Medical Monitor. If following consultation, the patient will receive an additional intravitreal ranibizumab 0.5 mg injection at the next scheduled Q4W study visit, and will then have the PDS implant (pre-filled with ranibizumab 100 mg/mL) surgically inserted 1-14 days after the intravitreal injection and within the same visit window.

After randomization (Day 1) and until the Week 56 visit (i.e., the comparator-controlled study treatment phase), patients randomized to the comparator arm who meet specific clinical criteria (development of CI-DME or PDR/ASNV; Section 4.3.2.3 of the Protocol) per Investigator assessment can be treated with supplemental intravitreal ranibizumab 0.5 mg injections. The Protocol criteria must be met for the first supplemental intravitreal ranibizumab treatment; subsequent supplemental treatments in the comparator arm can be done per Investigator discretion.

After the Week 64 visit (i.e., the PDS extension phase), comparator arm patients with the PDS implant who meet specific clinical criteria (development of CI-DME or PDR/ASNV) per Investigator assessment can receive supplemental treatment with intravitreal ranibizumab 0.5 mg injections per Investigator's discretion at any non-refill-exchange study visit during the study (see Section 4.3.2.3 of the Protocol).

In the PDS arm, all AEs will be collected after initiation of the first loading dose post-randomization.

In patients randomized to the comparator arm, prior to study drug initiation (either as a supplemental treatment prior to Week 60 or a loading dose), only the following AEs will be collected:

- Serious adverse events (SAEs) caused by a protocol-mandated intervention
- Severe acute respiratory coronavirus 2 (SARS-CoV-2)-related (due to viral infection or vaccine administration) AEs
- AEs leading to study discontinuation

After study drug initiation, all AEs will be collected.

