4. ANALYSIS SETS

The following populations are defined:

Table 1 Analysis Sets

Population	Definition
ITT Population	All patients who are randomized. Patients will be grouped according to treatment assigned at randomization.
Safety-Evaluable Population	All patients who receive any study treatment, and patients randomized to the comparator arm under observation, grouped according to treatment actually received prior to Week 52. In the PDS arm, the population includes all patients randomized to PDS receiving at least one loading dose, or any patient who received the PDS implant prior to Week 52. In the comparator arm, the population includes all patients randomized to the comparator arm who did not receive the PDS implant prior to Week 52.
PDS Safety Population	All patients who receive the PDS implant, including patients in the comparator arm who cross over to receive PDS at Week 64. Analyses on this population will only include data after first loading dose. Patients will be grouped according to treatment actually received prior to Week 52 (i.e. patients receiving PDS prior to Week 52 are grouped to the PDS arm, and patients receiving PDS after Week 52 are grouped to the comparator arm).
PDS PK Population	All patients who are randomized with at least one post implant PK sample available and who receive PDS at any time point, grouped according to treatment actually received prior to Week 52, and overall. Analysis is relative to time since implant insertion.

PDS PK Evaluable Population	All patients in the PDS PK Population excluding patients receiving intravitreal injections of ranibizumab in the study eye post PDS implant (including supplemental treatment) or patients with fellow eye ranibizumab after randomization, or bevacizumab treatment in either eye within 9 months prior to randomization or after randomization, or patients with septum dislodgment. Patients will be grouped according to treatment actually received prior to Week 52, and overall. Analysis is relative to time since implant insertion.
Aqueous Humor PK Evaluable Population	Subset of patients in the PDS PK Evaluable Population with at least one post implant aqueous humor PK sample. Patients will be grouped according to treatment actually received prior to Week 52,and overall.

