5.1 GENERAL CONSIDERATION

Efficacy analyses will be based on the intent-to-treat (ITT) Population unless otherwise specified.

Descriptive summaries will include the mean, standard deviation (SD), median, and range for continuous variables, and counts and percentages for categorical variables. Missing data for descriptive summaries will not be imputed unless otherwise noted.

For all efficacy endpoints, comparative efficacy analyses will be performed during the comparator-controlled treatment period (randomization through Week 60). At the primary

analysis, only the efficacy assessments collected through Week 52 will be included in the comparative efficacy analyses and descriptive summaries. At the final (end of study) analysis only the efficacy assessments collected through Week 60 will be included in the comparative efficacy analyses and data collected through end of study will be included in summaries. For the safety summaries, only data reported through Week 52 will be included at the time of the primary analysis. At the time of the final analysis, safety summaries will include all safety data collected through end of study (see Section 5.6).

Unless otherwise noted, analyses of efficacy outcome measures will be stratified by the randomization stratification factors (ETDRS-DRSS level [47 vs. 53] and intraretinal or subretinal fluid status on SD-OCT [present vs. absent] as assessed at baseline by a central reading center) as recorded in IxRS.

A nominal type I error penalty of 0.0001 (two-sided) will be taken for each time the iDMC conducts an unmasked interim safety review prior to the primary analysis. At the time of the primary analysis, four interim data reviews have been conducted by the iDMC; therefore, efficacy analyses will be performed at a significance level of 0.0496. All CIs will be two-sided and at the 95.04% level.

The occurrence of each type of intercurrent event as defined in Section 5.3.1 will be summarized by treatment arm. Additionally, the occurrence of each type of intercurrent event due to coronavirus disease of 2019 (COVID-19) as defined in the supplementary analysis in Section 5.3.3 will be summarized by treatment arm.

Data collected in selected scheduled and unscheduled visits will be mapped to visits that appear in the schedule of assessments (see Appendix 1 of the Protocol) per the Protocol using the actual study day of assessment.

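### Table 2 gives no safety or exposure window to comparator patients between Week 52 and first loading dose, or to never-implanted patients after Week 52, contradicting SAP Sections 5.1 and 5.6.2

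*SAP*

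**What the plan says.** Section 5.6 pairs each population with one analysis: "Safety-Evaluable Population at the time of the primary analysis through Week 52 and for the PDS Safety Population through the end of the study", the latter at the final analysis, subject to a general exception for anything specified elsewhere. Table 2 turns this into windows. The comparator row of the Safety-Evaluable Population reads "Day of randomization (Study Day 1) to Week 52 at the primary analysis". The comparator row of the PDS Safety Population reads "Day of 1st loading dose injection (PDS Day 1) (expected at the Week 60 visit) through EOS at the final analysis".

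Table 1 in Section 4 defines the PDS Safety Population as "All patients who receive the PDS implant, including patients in the comparator arm who cross over to receive PDS at Week 64", and adds: "Analyses on this population will only include data after first loading dose".

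Two other places promise more. Section 5.1 states: "At the time of the final analysis, safety summaries will include all safety data collected through end of study". Section 5.6.2 takes the start of the treatment-emergent period from Table 2 but ends it at study completion or premature discontinuation.

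On dosing, Section 1.2 allows supplemental ranibizumab in the comparator arm "After randomization (Day 1) and until the Week 56 visit". It then states: "Beginning at Week 60, patients will receive two loading doses with intravitreal ranibizumab 0.5 mg injections". Surgery follows the second of these injections.

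**The concern.** The two windows do not meet. In the comparator arm one closes at Week 52 and the other opens at about Week 60. A patient who is never implanted does not enter the second window at all.

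The data will exist, because Section 5.6 collects all adverse events in comparator patients once ranibizumab has started. A programmer working from Table 2 would leave these events out of the final tables of ocular and non-ocular AEs and SAEs, events of special interest, APTC events and deaths. A programmer working from Section 5.1 would include them.

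The omission may also depend on outcome. A comparator patient who is loaded at Week 60 and then has a serious event, withdraws or dies before surgery never joins the PDS Safety Population. The event that prevented the implant would then be missing from the final frequency tables.

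**Working it through.** The SAP states no figure for this gap, so there is none to reproduce. The check compares windows with populations.

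**Inputs (all from the SAP)**
- Safety-Evaluable window: ends at Week 52, primary analysis only (Section 5.6, Table 2).
- PDS Safety window, comparator arm: opens at first loading dose, expected Week 60 (Table 2).
- PDS Safety membership: implanted patients only, data after first loading dose only (Section 4, Table 1).
- Comparator arm: about 60 patients (Section 1.2.1).
- Dropout: about 5% when recruitment closed; 15% by Week 52 assumed in planning (Section 3).

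**Coverage after Week 52**

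| Group | Window in Table 2 |
|---|---|
| PDS arm, implanted | Continuous, first loading dose to end of study |
| Comparator, later implanted, Week 52 to first loading dose | None |
| Comparator, later implanted, from first loading dose | PDS Safety Population |
| Comparator, loaded but not implanted | None |
| Comparator, never loaded | None |
| PDS arm, loaded but not implanted | None |

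**Size of the comparator gap**
- Length = 60 − 52 = 8 weeks.
- No dropout: 60 × 8 = 480 patient-weeks; 480 / 52.18 = 9.2 patient-years.
- 5% dropout: 57 × 8 = 456 patient-weeks = 8.7 patient-years.
- 15% dropout: 51 × 8 = 408 patient-weeks = 7.8 patient-years.
- Share of the planned 60 weeks before loading = 8 / 60 = 13%.

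For never-implanted patients the gap runs from Week 52 to end of study. The SAP gives neither their number nor a fixed end date, so no person-time can be calculated.

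**Whether another section fills the gap**
- Section 5.6.1 ties exposure to the Table 2 schedule. It includes injections given before the implant, but in the PDS Safety Population Table 1 removes anything before first loading.
- Section 5.5.5 counts comparator supplemental injections only to Week 52.
- Sections 5.5.4 and 5.4.2.14 concern the period after implant.
- Section 5.7.1 splits concomitant medication by the same two populations and periods.
- A supplemental injection cannot serve as PDS Day 1, because Section 5.6 distinguishes supplemental treatment from a loading dose.
- Section 5.2 (disposition over the whole study) and Sections 5.4.2.3 to 5.4.2.5 (time to event through Week 60) do cover the period, but they report neither adverse events nor exposure.

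**The case against.** The best defence is that the SAP never decides to discard these data. Each Safety-Evaluable row of Table 2 is labelled as applying at the primary analysis, so the table is silent about that population at the final analysis rather than excluding it. The text introducing Table 2 fixes only start dates. Section 5.6.2 runs to study completion, Section 5.1 promises everything, and the general exception in Section 5.6 could let Section 5.1 prevail. This stands in part: the defect is a contradiction, and a reader who infers a settled plan to drop data goes too far. It does not close the gap. Section 5.1 refers back to Section 5.6 for its detail, and no bridging window is specified anywhere.

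It can also be said that the safety objective concerns ranibizumab delivered by the implant, so an implanted-only final population fits it. That is fair for the main final summary. It does not account for patients given loading injections in preparation for the implant, or for the promise in Section 5.1.

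Three stronger readings are tempting and not supported.
- That the data vanish from every table. Disposition and the Week 60 time-to-event analyses still cover the period.
- That only the comparator arm is affected. PDS-arm patients who were loaded but never implanted also lose their events after Week 52, though supplemental ranibizumab in that arm is described as given post implant.
- That a count of lost injections can be given. The SAP states no rescue rate, and its wording does not settle whether the Week 56 visit itself is included.

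Finally, comparator patients who have had no ranibizumab have only three limited categories of adverse event collected: SAEs caused by a mandated intervention, SARS-CoV-2-related events, and events leading to study discontinuation. Most of the 9.2 patient-years may therefore carry little safety information.

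**Conclusion.** The point holds as an internal contradiction with a practical consequence. Section 5.6 and Table 2 cannot deliver what Sections 5.1 and 5.6.2 promise. Followed literally, they leave two blocks out of the final safety and exposure tables.

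- Comparator patients from Week 52 to first loading. The 8-week gap assumes loading at the planned visit, and the patient-years assume about 60 patients with the dropout shown. The part that matters is the share contributed by patients already given supplemental ranibizumab, which is unknown.
- Never-implanted patients in both arms, for all data after Week 52. This includes comparator patients given Week 60 or 64 injections without surgery. Their number is unknown and may be small, but their missing data may be related to safety.

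The primary and key secondary efficacy analyses, the significance level and the Week 52 safety comparison are untouched.

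**What to change.** Add final-analysis rows for the Safety-Evaluable Population to Table 2.
- Comparator patients later implanted: randomization to the day before the first loading dose, after which the PDS Safety Population takes over.
- Patients never implanted, in either arm and whether or not they had loading injections: Study Day 1 to end of study. Assigning on implant status alone gives each patient one end date.

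Use the same windows for exposure in Section 5.6.1, and extend Section 5.5.5 to the first loading dose at the final analysis. Then make Sections 5.1, 5.6 and 5.6.2 state the same end of follow-up. In the new comparator rows, note that adverse event collection is limited until ranibizumab starts, so that a low count there is not read as a low rate.

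The cost is a few table rows, matching text edits and one rerun of existing descriptive tables at the final analysis. No new data are needed.
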